#### MOVE-IT HEP Home Visit 3 (will last about 90 minutes)

- At the end of the HEP period, a non-blinded team member will conduct a home visit at the patient's residence to recover the system hardware. Prior to recovery, a therapist will observe patients' independent use of the system either in the home or via an approved telehealth connection.
- Participants will respond to usability assessment instruments including:
  - System Usability Scale (SUS)
  - o Technology acceptance model (TAM) questionnaire
  - Short response open-ended narrative questions.

These assessments will be audio recorded using Zoom. The recordings will be stored in secure folders on O/drive at UVA and Duke Box, that only the research team has access to. The interview recording will only identify subjects with their subject ID. Transcriptions will be reviewed by a member of the research team for accuracy. Once reviewed and transcribed, all identifiable information will be removed and only the de-identified transcript will be stored and used for analysis. Another member of the research team will perform a quality check of the transcript to ensure accuracy.

#### **GROUP 2: UCT GROUP:**

- Participants in the control group will continue to receive any previously prescribed therapy services. These patients will not receive any treatment services through the study as UCT group participants.
- At least once every two weeks during the interventional period, non-blinded study staff will contact the participant by phone or HIPAA compliant video conferencing to collect self-reported adherence data and confirm that no change in medical status has occurred that would impact continued participation.

#### ALL - Outpatient Visit 2: Post-Assessment (will last about 90 minutes)

- Conducted at end of 10-week intervention period.
- Blinded study therapist will administer the same battery of tests used in pre-assessment.

#### ALL - Outpatient Visit 3: Follow-up Assessment (will last about 90 minutes)

- Conducted approximately 3 months after Post-Assessment.
- Blinded study therapist will administer the same battery of tests used in pre- and post-assessment.

To promote equipoise, parents of children in the UCT group will be provided free access to the MOVE-IT HEP following completion of the control protocol. When participation in the study is completed, all subjects will return to usual care under their individual health care provider.

A graphical summary of the MOVE-IT Phase II study is provided in Figure 2 below.

[figure not shown]

Figure 2. MOVE-IT Phase II Study Plan

# 6.2 Laboratory EvaluationsNo laboratory evaluations will be conducted under this study.

#### 7 STATISTICAL CONSIDERATIONS

#### 7.1 Study Outcome Measures

# 7.2 Sample Size Considerations

Power analysis for the study is based on approximate effect size and variance information derived from previous RCTs involving intensive therapy for children with hemiplegia. In particular, JTHF outcomes reported by Klingels et al. provide approximate effect size and variance. For the Wilcoxon Mann-Whitney test, if 20 subjects per group (40 total) complete the protocol, we will have at least 0.80 power ( $\alpha$ <0.05) if the true underlying probability that the MOVE-IT pre-to-post intervention change in JTHFT score is greater than the pre-to-post change for UCT is 0.75 or greater. Recruitment of 24 subjects per group will allow a conservative 15% dropout rate (e.g. compared to the CHAMP R01 program RCT, NCT01895660), which assumed 10%).

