#### 4 STUDY DESIGN

The study is a randomized control study.

Following screening, enrolled subjects will be randomized to either the MOVE-IT home exercise program (HEP) or usual care treatment (UCT) group using a centralized and masked process developed by the study biostatistician. The HEP group is the interventional group. The UCT group is the control group. Following the control strategy previously adopted in the Children with Hemiparesis Arm and Movement Project (CHAMP) multi-site RCT (NICHD R01, trial registration number NCT01895660), children in the UCT group will be followed as they continue to receive their previously prescribed therapy services. As UCT group participants, these children will not receive any treatment services through the study. Parents will be asked to report therapy services their children receive during each assessment visit.

To ensure that an approximately equal number of subjects are randomized to the MOVE-IT HEP and UCT groups throughout the Phase II enrollment period, we will randomly assign the patients to the two study-groups in accordance with a permuted block randomization scheme. The randomization list will be generated by a UVA study biostatistician ([name]) using the PLAN procedure of SAS (SAS Institute Inc., Cary, NC). One subject randomization table will be generated for each site. The group assignment will be blinded to the therapists (raters) who perform the pre- and post-assessments. The group assignment will be not be blinded to the participants. The non-rater members of the IRB-approved study team will have access to the randomization list.

Demonstration of statistically significant improvement in UE motor function for participants the MOVE-IT HEP versus UCT will support the validity of MOVE-IT use as an intervention for children with hemiplegia. In home use, MOVE-IT will enable more frequent and intensive therapy with reduced travel and may extend the service range of existing rehabilitation providers to include underserved areas. In clinical practice, MOVE-IT will enable new models of delivery based on remote monitoring combined with outpatient services, increasing quality and efficiency of care. Statistical considerations for sample size determination, primary analysis, and secondary analyses are described below.

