#### 7.4 Analysis Plan

Primary variable analysis involves analysis of completion times for each of the seven tasks in the JTHFT which will be summed to produce a total score. The pre-intervention scores will be subtracted from the post-intervention scores to produce a set of delta values. These delta values scores ( $\Delta$ ) will be analyzed via Analysis of Covariance (ANCOVA). One null hypothesis will test if the mean pre-to-post-intervention change in the total JTHFT score is equal to zero, while the second null hypothesis will test if the mean pre-to post-intervention change in the JTHFT score is the same for patients who participate in a 10-week MOVE-IT HEP and patients who under UCT over the same duration. For both null hypotheses, a p $\leq$ 0.05 decision rule will be utilized as the rejection criterion. Analysis of data from the 3-month follow-up assessment will be performed in a similar manner.

Secondary variable analysis includes analysis of the pre-to-post intervention changes in the composite WMFT scores which will be analyzed in the same way as the pre-to-post intervention change in the composite JTHFT scores. The same method of analysis will be used to analyze the pre-to-post intervention changes in the QUEST scores.

The Likert scale responses to the SUS questionnaire will be summarized per question, and per question category, by frequencies and percentages. As an overall measure of system usability, a composite SUS score in the range from 0 to 100 will be derived from individual responses. By convention, a SUS score greater than or equal to 68 is indicative of an efficient, effective, and satisfying system. For the TAM questionnaire, percentages of favorable responses to the questions of each topic will be estimated via a binomial generalized estimating equation model, and a 90% confidence interval constructed. A Wald test will be used to test the null hypothesis that the odds of a favorable response are independent of the question topic.

Therapy session adherence and activity will be assessed by way of a binomial generalized estimating equation model, in which therapy adherence and activity measures (collected via parental logs) will be compared between the patients who participate in a 10-week MOVE-IT HEP and patients under UCT over the same duration.

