All biostatistical design and analysis will be conducted by [name], a Pstat accredited Senior Biostatistician within the Department of Public Health Sciences of the University of Virginia School of Medicine.

Data from the UVA and Duke sites will be combined during analysis. Randomization will be done at each site. Variation between the two sites is expected to be minimal. The effect of the treatment to be tested is expected to be the same among the two sites, which

will use identical protocols.

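### The only stated power (at least 0.80) is for a Wilcoxon-Mann-Whitney test, but the planned primary test is an ANCOVA of mean change in JTHFT time

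*Combined protocol and SAP*

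**What the plan says.** Section 7.2 sizes the trial on a rank test: "For the Wilcoxon Mann-Whitney test, if 20 subjects per group (40 total) complete the protocol, we will have at least 0.80 power". The effect is a probability of 0.75 or more that the MOVE-IT change in JTHFT is greater than the usual-care change. The section opens by saying "Power analysis for the study is based on approximate effect size and variance information derived from previous RCTs" and points to one earlier trial, but prints no mean difference, SD or correlation.

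Section 7.4 sums the seven JTHFT task times, subtracts the pre-intervention total from the post-intervention total, and analyses the result by ANCOVA. The between-group hypothesis concerns means: "the second null hypothesis will test if the mean pre-to post-intervention change in the JTHFT score is the same" in the two arms. No covariate is named. No Wilcoxon test or rank transformation appears as primary, sensitivity or fallback analysis.

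On sites, section 4 says "One subject randomization table will be generated for each site". The end of section 7.4 pools the two sites, on the ground that "Variation between the two sites is expected to be minimal".

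**The concern.** The two sections concern different quantities. The rank test addresses how often a child in one arm changes more than a child in the other. The ANCOVA addresses a difference in mean seconds. A probability of 0.75 fixes neither the mean difference nor the SD, so the power of the planned test cannot be derived from what is printed. A reader cannot tell what difference in JTHFT time the trial was sized to detect. The test that justifies the sample size would never be reported.

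Direction and sidedness are also open. Under section 7.4 a faster child has a negative change, whereas section 7.2 powers on the MOVE-IT change being the greater one. Neither section says whether the 0.05 level is one-sided or two-sided.

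**Working it through.** **Inputs from the documents.** 20 completers per arm (N = 40), P = 0.75, power at least 0.80, alpha 0.05 (section 7.2); ANCOVA of change (section 7.4); about 1:1 allocation, randomized by site (section 4). Two-sided testing is assumed.

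**1. The plan's own figure.** Noether's formula: power = Φ(√(12·N·c(1−c))·|P−0.5| − 1.96), with c = 0.5.
- √(12 × 40 × 0.25) × 0.25 = 2.739, and Φ(2.739 − 1.960) = 0.782.
- N for 0.80 power = (1.960 + 0.842)² / (12 × 0.25 × 0.0625) = 41.9, against 40 in the plan.
- Simulated under a normal shift (20,000 runs), the rank test has power 0.816.

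So at least 0.80 is a fair figure for the rank test. One-sided, the formula gives 0.863, which does not match. Recruitment also agrees: 20 / 0.85 = 23.5, rounded up to 24 per group.

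**2. The planned test with normal changes.** If changes are normal with equal variance, P = Φ(d/√2), so d = √2 × 0.6745 = 0.954. The noncentrality is 0.954 × √(20/2) = 3.016.
- t-test, 38 df: 0.836.
- ANCOVA with an uninformative baseline, 37 df: 0.836; with site as well, 36 df: 0.835. Simulated values are about 0.83.
- If baseline explains 10, 25 or 50% of the variance of change (assumed), simulated power is 0.86, 0.92 or 0.98.

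**3. The planned test with a skewed baseline.** Two assumed models were used, each calibrated to P = 0.75, with baseline and site in the ANCOVA and 20,000 runs per cell.
- Proportional change: log post = log pre − δ (MOVE-IT arm only) + error, with error SD 0.15 to 0.4.
- Additive change: normal change, SD 5 to 15 s, on a lognormal baseline with median 100 s.

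| Baseline log-SD | 95% baseline range, exp(3.92 × log-SD) | ANCOVA, proportional | ANCOVA, additive | Rank test |
|---|---|---|---|---|
| 0.4 | about 5-fold | 0.79–0.81 | 0.82–0.83 | 0.81–0.82 |
| 0.7 | about 16-fold | 0.75–0.76 | 0.82–0.83 | 0.81–0.82 |
| 1.0 | about 50-fold | 0.66–0.67 | 0.82–0.83 | 0.81–0.82 |

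With P fixed, the rank test hardly moves, while ANCOVA power moves in both directions.

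**4. What a restated section 7.2 would look like.** At 20 per arm with baseline and site fitted (36 df), 0.80 power needs a mean difference of 0.91 residual SD. Once baseline is a covariate, analysing change or the post score gives the same arm effect, so the residual SD is the post-score SD × √(1−r²), where r is the correlation between baseline and post score. For assumed r of 0.5, 0.7 and 0.9, the difference needed is 0.79, 0.65 and 0.40 post-score SD.

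**5. The site term.** Simulated with normal changes, an uninformative baseline and arms balanced within site:

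| Site difference (SD of change within site) | Power without / with site | Type I error without / with site |
|---|---|---|
| 0 | 0.83 / 0.83 | 0.05 / 0.05 |
| 0.5 | 0.80–0.81 / 0.82–0.83 | about 0.04 / 0.05 |
| 1.0 | 0.75–0.76 / 0.82–0.83 | about 0.03 / 0.05 |

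With no site effect, adding site costs about 0.002 of power at most. With a site effect, leaving it out counts the site difference as noise: the test becomes conservative and the intervals too wide.

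**The case against.** **No deficit is shown.** With normal or additive change, ANCOVA power is 0.82 or more. The clearest shortfall in the table needs proportional change and a roughly 50-fold spread of baseline times, for which the documents give no figure. This stands. A reader might infer that the trial is underpowered, but the documents do not support that. Other assumed shapes, with heavy tails or a strongly skewed change, can push ANCOVA power lower still, and they too are assumptions.

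**A rank-based calculation is a safe proxy for ANCOVA.** It is, for normal changes with a prognostic baseline. The plan does not make that argument and names no covariate, and the argument fails when change is proportional to a skewed baseline.

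**A null result is read from the estimate and its confidence interval.** Correct. The mismatch biases neither the estimate nor the type I error. It is a gap in the justification of the sample size.

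**The plan gives a reason for pooling sites.** It does, but as an expectation. Pooling the data does not conflict with fitting a site term, and the term costs almost nothing if the expectation proves right.

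**Then make the rank test primary.** A reader might infer this remedy. It would not test the mean-change hypotheses in section 7.4, and it would drop the covariates. Section 7.4 also applies the primary method to WMFT, QUEST and the 3-month data, so the change would spread well beyond one sentence.

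**Conclusion.** The mismatch is real, and no other section reconciles it. The 0.80 is sound for the Wilcoxon-Mann-Whitney test but is not the power of the planned ANCOVA. At P = 0.75 and 20 per arm, that power is about 0.83 to 0.84 with normal changes and an uninformative baseline, higher with a prognostic baseline, and about 0.66 to 0.81 with change proportional to a skewed baseline. These figures rest on assumed distributions and two-sided testing. They show that the stated figure does not carry over to the planned test, not that power is inadequate. The point should be fixed, as a correction to the sample-size justification together with a small gain from specifying the model.

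**What to change.** Before outcome data are seen by group:

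1. **Section 7.2.** Restate power for the ANCOVA, giving the assumed mean difference in JTHFT time, residual SD, baseline correlation, sidedness and direction (improvement is a negative change under section 7.4). Do this even if the figure becomes less favourable than 0.80. The 0.91 residual SD above can serve as the template.
2. **Section 7.4.** Name baseline JTHFT total and site as the ANCOVA covariates, site because randomization is done separately at each site.
3. **Optional.** Report the Wilcoxon-Mann-Whitney test as a prespecified sensitivity analysis, so that the test used for sizing is seen in the results. This does not replace item 1.

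The cost is wording in two sections and at most one extra analysis, with no new patients or data. The downsides are slightly more analysis and a possibly less favourable stated power.

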## 7.3 Participant Enrollment and Follow-Up

Approximately 24 subjects will be recruited at each of the two sites (48 total). Recruited children will have a diagnosis of hemiplegia resulting from cerebral palsy, stroke, or other form of brain injury; be between 4 and 14 years of age; have no history of uncontrolled seizures; and be medically stable. Children will be excluded if they received botulinum toxin injections, stem cell infusions or another form of intensive UE therapy, such as CIMT, within the prior 6 months. Children may receive other forms of treatment or intervention during and after the MOVE-IT intervention; data about such other interventions will be collected prospectively from parents.

It is expected that participant enrollment in the MOVE-IT Phase II RCT will be open for a period of approximately 10 months. Monthly enrollment is projected to average from 6-12 new subjects per month across both sites. Each subject's participation includes a 10-week interventional (or control) period and a 3-month follow-up assessment.

An approximately equal number of subjects will be recruited at the UVA Children's Hospital (n=24) and the Duke Children's Hospital (n=24) study sites, facilitated by experienced study coordinators at each site. Based on recent completion of studies of similar scope, including the CHAMP CIMT trials at UVA [12], the team anticipates being able to meet the MOVE-IT RCT goals.

#### 7.4 Analysis Plan

Primary variable analysis involves analysis of completion times for each of the seven tasks in the JTHFT which will be summed to produce a total score. The pre-intervention scores will be subtracted from the post-intervention scores to produce a set of delta values. These delta values scores ( $\Delta$ ) will be analyzed via Analysis of Covariance (ANCOVA). One null hypothesis will test if the mean pre-to-post-intervention change in the total JTHFT score is equal to zero, while the second null hypothesis will test if the mean pre-to post-intervention change in the JTHFT score is the same for patients who participate in a 10-week MOVE-IT HEP and patients who under UCT over the same duration. For both null hypotheses, a p $\leq$ 0.05 decision rule will be utilized as the rejection criterion. Analysis of data from the 3-month follow-up assessment will be performed in a similar manner.

Secondary variable analysis includes analysis of the pre-to-post intervention changes in the composite WMFT scores which will be analyzed in the same way as the pre-to-post intervention change in the composite JTHFT scores. The same method of analysis will be used to analyze the pre-to-post intervention changes in the QUEST scores.

The Likert scale responses to the SUS questionnaire will be summarized per question, and per question category, by frequencies and percentages. As an overall measure of system usability, a composite SUS score in the range from 0 to 100 will be derived from individual responses. By convention, a SUS score greater than or equal to 68 is indicative of an efficient, effective, and satisfying system. For the TAM questionnaire, percentages of favorable responses to the questions of each topic will be estimated via a binomial generalized estimating equation model, and a 90% confidence interval constructed. A Wald test will be used to test the null hypothesis that the odds of a favorable response are independent of the question topic.

Therapy session adherence and activity will be assessed by way of a binomial generalized estimating equation model, in which therapy adherence and activity measures (collected via parental logs) will be compared between the patients who participate in a 10-week MOVE-IT HEP and patients under UCT over the same duration.

All biostatistical design and analysis will be conducted by [name], a Pstat accredited Senior Biostatistician within the Department of Public Health Sciences of the University of Virginia School of Medicine.

Data from the UVA and Duke sites will be combined during analysis. Randomization will be done at each site. Variation between the two sites is expected to be minimal. The effect of the treatment to be tested is expected to be the same among the two sites, which

will use identical protocols.

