#### 5 STUDY POPULATION

#### 5.1 Selection of the Study Population

Ages: 4 - 14 years (inclusive)

Sex: Any Race: Any

Target # of subjects (at all sites) needed to complete protocol: 40.

Expected rate of screen failure/ dropouts/withdrawals from all sites: 15%.

Number of subject/dyads to be enrolled at all sites: 48.

Number of subjects who will sign a consent form under this protocol: 48 dyads.

(24 at UVA and 24 at Duke)

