#### 5.2 Inclusion/Exclusion Criteria

#### Criteria for inclusion

- (1) Diagnosis of hemiplegia resulting from cerebral palsy, stroke, or other form of brain injury;
- (2) Medically stable;
- (3) Manual Abilities Classification System (MACS) rating between II and V; indicating the child experiences mild to severe difficulty in handling objects with the affected hand;
- (4) Communication Functional Classification System (CFCS) rating between I and III; indicating the child usually communicates effectively with familiar communication partners, but not unfamiliar partners, in most environments;
- (5) Participant has antigravity strength in the affected UE at the elbow to at least 45 degrees of active flexion;
- (6) Participant has antigravity shoulder strength in the affected UE to at least 30 degrees each in active flexion, abduction/adduction, and 15 degrees in active internal/external rotation when in an upright and seated position;
- (7) Participant has ability to perform a basic color-matching test and identify characters on a vision chart;

- (8) Participant must be available to attend study visits;
- (9) Willingness and ability to comply with scheduled visits and study procedures.

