#### **6 STUDY PROCEDURES/EVALUATIONS**

# 6.1 Study Procedures

Identical procedures will be followed at the UVA and Duke sites.

Prior to consent, candidates will be contacted by phone and the parent/guardian asked to respond to questions pertaining to eligibility (inclusion/exclusion criteria). For example:

- Does the child have a history of uncontrolled seizures?
- Has the child received botulinum toxin injections, stem cell infusions or another form of intensive arm therapy, such as CIMT, within the prior 6 months?
- Can the child move the affected arm and flex the elbow about halfway?
- Is the child's corrected vision good enough to comfortably watch a TV show for 30 minutes?

The final list of questions will be included in a telephone recruitment scripts that will be submitted for IRB approval prior to use. After prescreening using the IRB-approved script, candidates will be scheduled for a remotely-administered consent and screening telehealth visit and for a pre-assessment visit.

- The parent/guardian will be asked to complete the following parental report instrument:
  - o Pediatric Motor Activity Log (inventory of child's functional use of the UE)

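### Does the primary JTHFT total need a written score for a task that a child cannot finish?

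*Combined protocol and SAP*

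**What the plan says.** Section 7.4 describes "analysis of completion times for each of the seven tasks in the JTHFT which will be summed to produce a total score", subtracts the baseline total from the post-intervention total, and analyses the differences by ANCOVA. It contains no time limit, no code for inability and no missing-data rule. Section 7.1 (Study Outcome Measures) is a heading with no text in the supplied document.

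On entry, section 5.2 accepts "Manual Abilities Classification System (MACS) rating between II and V; indicating the child experiences mild to severe difficulty in handling objects". Its strength minimums concern the elbow ("Participant has antigravity strength in the affected UE at the elbow to at least 45 degrees of active flexion") and the shoulder. None concerns the hand. An example telephone question in section 6.1 is "Can the child move the affected arm and flex the elbow about halfway". Section 5.2 also requires "Willingness and ability to comply with scheduled visits and study procedures". At Outpatient Visit 1 the blinded therapist checks eligibility again in person before the child is allocated. A child whose testing is interrupted may be asked to come back.

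On numbers, section 5.1 states "Target # of subjects (at all sites) needed to complete protocol: 40" and "Expected rate of screen failure/ dropouts/withdrawals from all sites: 15" percent, with 48 enrolled. Section 7.2 states that "if 20 subjects per group (40 total) complete the protocol, we will have at least 0.80 power", for a Wilcoxon Mann-Whitney test when the probability of a greater change under MOVE-IT is 0.75.

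Section 3 requires blinded assessors who are certified for the instruments. Section 6.1 says both sites follow the same procedures.

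**The concern.** A task that is never finished has no completion time, so a sum of seven times is undefined for that child, and so is the change. The entry criteria make this plausible, because nothing in section 5.2 sets a floor on hand function.

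Three things could be at stake.

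- **Power.** The 15% allowance names screen failure, dropout and withdrawal. It leaves almost no room for a child who attends every visit but has no total.
- **Population.** Leaving out children who cannot do a task at baseline narrows the trial to the less impaired. It also discards any child who gains a task during treatment.
- **Bias.** A child who finishes all tasks at baseline but not at week 10 has a poor outcome after allocation. Omitting such children from usual care would dilute a true effect. Omitting them from MOVE-IT would favour it.

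A rule left unwritten might also be chosen after results are known.

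**Working it through.** **Inputs from the documents.** 40 completers, 20 per group; probability 0.75; alpha 0.05, taken as two-sided because the sidedness is not stated; 15% loss; 48 enrolled. **Assumptions.** A normal shift in the change score. The share of completers with no total is not in the documents, so 5%, 10% and 20% are shown.

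**1. The plan's own figures.**

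- Enrolment: 40 / 0.85 = 47.06, which rounds up to 48 in two equal groups. Expected completers: 48 × 0.85 = 40.8, a margin of 0.8 of a child.
- Shift matching probability 0.75: √2 × 0.6745 = 0.954 SD.
- Noether's formula: power = Φ(0.25 × √(3 × 40) − 1.96) = 0.78.
- Exact Wilcoxon by simulation: 0.82.
- Two-sample t test on the change, standing in for ANCOVA with no gain from a covariate: 0.84.

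The stated 0.80 is reproduced within the spread of the methods.

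**2. Power if children without a total are left out.**

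| No total | Totals left | Noether | Exact Wilcoxon | t test |
|---|---|---|---|---|
| 0% | 40 | 0.78 | 0.82 | 0.84 |
| 5% | 38 | 0.76 | 0.80 | 0.82 |
| 10% | 36 | 0.74 | 0.77 | 0.79 |
| 20% | 32 | 0.69 | 0.71 | 0.74 |

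A baseline covariate would offset some of this. If it correlates 0.3 with the change, ANCOVA power is 0.83 with 36 totals. At correlation 0.4 it is 0.81 with 32. The plan names no covariate, so these correlations are assumptions too.

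**3. Power if the same children are scored at a fixed maximum.** As a simplification, a child unable at both visits gets the maximum twice, so the change is zero. All 40 are analysed, with mean change in usual care set to zero. The Wilcoxon columns use the large-sample test, so they differ slightly from the exact values above.

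| Unable | Wilcoxon, left out | Wilcoxon, fixed maximum | t test, left out | t test, fixed maximum |
|---|---|---|---|---|
| 10% | 0.78 | 0.75 | 0.79 | 0.78 |
| 20% | 0.71 | 0.67 | 0.74 | 0.72 |

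On this simplification the fixed maximum gains nothing in power.

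A richer simulation let some children regain a task. It rests on many hypothetical inputs (task times, their spread, rates of regaining a task). With 20% unable at baseline, power was 0.65 to 0.69 when they were left out, 0.75 to 0.84 with a 90 s limit, 0.70 to 0.82 with 120 s, and 0.61 to 0.78 with 180 s. The result depends on the limit chosen and on the assumed inputs.

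**4. Worst-case bias.** Suppose the children lost at week 10 are exactly those with the largest worsening, all in one arm of 20 (t test).

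- One lost from usual care: the mean effect falls from 0.957 to 0.859 SD, and 1 − 0.859/0.957 = 10%. Power falls from 0.84 to 0.77.
- Two lost from usual care: 1 − 0.775/0.957 = 19%. Power is 0.69.
- No true effect, one or two lost from MOVE-IT: two-sided type I error rises from 0.05 to 0.07 or 0.10.

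These are upper bounds, because they put every loss in one arm and at the extreme of the distribution.

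**The case for a change.** The strongest case for a change is that the endpoint is undefined for some admissible children. None of the safeguards supplies a number: trying a task may count as compliance, a return visit does not help a child who is unable, and no manual is cited. Leaving the child out, capping the time and summing fewer tasks give different primary estimates. Writing the rule down would be cheap, and the biostatistician who produces the randomization list is not described as blinded.

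The description of the gap stands. So does the arithmetic showing that the allowance has no slack. Four points keep this from requiring a change.

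- The plan is silent on these children; it does not say to exclude them. That the sample size counts them as completers is an inference. Completing the protocol in section 7.2 can as well mean having the required assessments.
- Visit 1 includes an in-person eligibility check before allocation, and ability to comply with procedures is a criterion. A child who cannot do the primary test could be a screen failure there, which the 15% covers. The text permits this reading without compelling it.
- Raters are certified and blinded to group, so a convention applied at testing is applied without knowledge of the arm. Whether their training fixes a limit cannot be seen from the documents, and section 7.1 has no visible text.
- The bias route needs a medically stable child to lose a task within ten weeks. Staff ask about changes in medical status at least every two weeks in both groups. This does not exclude variable performance, but no document figure suggests it is common.

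**Conclusion.** No change to the plan follows. This is an unwritten scoring convention that certified, blinded assessors and the study biostatistician would be expected to fill sensibly. It is not an error in the design or in the stated power, which reproduces at 0.78 to 0.82 for the Wilcoxon test with 40 totals.

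If 5% to 10% of completers had no total and were left out, power would be about 0.74 to 0.82 across the three methods. At 20% it would be 0.69 to 0.74. The documents give no failure rate, and if nearly every child finishes all seven tasks the effect is negligible. The bias figures (type I error up to 0.10, dilution up to 19%) describe a constructed worst case.

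Nor is one rule shown to be better. With zero change for unable children, a fixed maximum gives slightly less power than leaving them out. Where children regain tasks it can give more or less, depending on the limit. A limit also hides change beyond it, and a long one adds variance. The choice is a trade-off that the documents' figures cannot settle.

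This conclusion assumes that one convention is applied alike at both sites and all visits, as the commitment to identical procedures implies, and that it is settled without regard to results by arm.
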